## 9. Research Methods

### 9.1 Study Design

To characterise the safety and efficacy profile of Blincyto and to describe drug utilisation and medication errors in routine clinical practice, this multi-centre study will be conducted as an observational study involving detailed retrospective medical record review of patients who initiated Blincyto in a routine clinical setting. Because this study will involve medical record review, it is not anticipated to have an effect on treatment practices while still allowing the collection of routinely monitored safety and efficacy outcomes.

### 9.2 Setting and Study Population

This medical record review study is expected to be conducted in cancer treatment centres in selected countries in Europe. Inclusion of specific European countries in the study will be dependent on local feasibility and local regulatory and ethics requirements. These treatment centres with a focus on treating subjects with ALL in participating countries will be recruited as sites for inclusion in the study. It is expected that larger centres will tend to be recruited since the patient population eligible for Blincyto is expected to be small, highly unique and most likely to be treated in larger centres. However, an attempt will be made to include smaller centres to aid representativeness.

The medical records of all patients initiating Blincyto at participating clinical sites in Europe will be eligible for abstraction. If required, informed consent will be solicited from the patient/next-of-kin/body as appropriate in line with local laws and regulations.

#### 9.2.1 Study Period

The start of the study will commence at the first data abstraction of the first site. Charts for new eligible patients at each site will be included during the first 5 years of study.

Chart abstractions for each eligible patient will continue for a minimum of 2 years post Blincyto initiation. End of Study will be approximately 7 years after the first patient was enrolled, at which point the vast majority of still active patients will have their minimum of 2 years of follow-up.

### **9.2.2 Selection and Number of Sites**

Cancer treatment centres will be eligible for selection after country-specific reimbursement of Blincyto and adopted by the treatment centre. It is expected that larger centres that specialize in treating patients with ALL will be most likely included but an effort will be made to include smaller centres to aid representativeness. It is estimated that at least 70 sites may be required to achieve a maximum number of approximately 300 patients and to provide diversity in the type and geographic location of sites. Countries assessed for participation will most likely include those to be among the earliest for launch of Blincyto and where it is allowable to observe patients in clinical practice following initiation of Blincyto treatment. The earliest sites will be able to provide up to 21 chart abstractions during the estimated 7-year study period; however, due to the staggered launch of Blincyto, later starting sites will perform fewer abstractions.

### **9.2.3 Patient Eligibility**

#### **9.2.3.1 Inclusion Criteria**

- Medical records of patients initiating Blincyto after country-specific reimbursement in routine clinical practice will be eligible for abstraction.

#### **9.2.3.2 Exclusion Criteria**

- Medical records of patients who have participated in Blincyto clinical trials will be excluded since their treatment will be prescribed by the study protocol unless the patient is receiving new Blincyto treatment outside the clinical trial.
- Medical records of patients participating in other Amgen non-interventional prospective studies in which safety endpoints are collected will be excluded
- Medical records of patients who have received Blincyto via an expanded access/compassionate use program will be excluded
- In countries where informed consent is required for access to medical records (in line with local laws and regulations): if such consent is not provided but is mandatory, the patient will be excluded.

### **9.2.4 Chart Abstraction**

Medical charts at sites will be reviewed once sites have been included in the study and then every 4 months thereafter until each eligible patient has been followed-up for a minimum of 2 years post Blincyto initiation. Charts for new eligible patients at each site

will be included during the first 5 years of study. The final analysis cohort will be constructed from the separate chart reviews documenting data in the patient's history from primary disease diagnosis until the earliest occurrence of the following events: death, withdrawal of consent, end of available data in the chart, or end of study. Medical history dates may pre-date primary diagnoses dates. Data to be extracted include variables relating to data since primary disease diagnosis, during Blincyto treatment and following completion of Blincyto treatment until end of observation or end of study, whichever is earlier. Data to be collected at each stage are listed in Section 9.3.

### 9.3 Variables

All data (including exposure, outcomes, and covariates) will be abstracted from the medical records and will include demographics, comorbidities, primary disease characteristics and treatment, allogeneic HSCT, concomitant medications, primary and secondary endpoints described in Section 9.3.2, covariates described in Section 9.3.3 and subgroup characteristics described in Section 9.7.2.3.4. Data to be collected is described below and summarised in Appendix B.

#### 9.3.1 Exposure Assessment

All patients included in this study will be or will have been exposed to Blincyto at their entry into the study. Exposure will be described in several ways:

- Duration of exposure (in days)
- Total cumulative dose ( $\mu\text{g}$ )
- Number of cycles completed (0-5)

#### 9.3.2 Outcome Assessment

##### 9.3.2.1 Primary Endpoint/Outcome

- Incidence of specified AEs (overall, and by severity and seriousness) – All AEs occurring during blinatumomab treatment and up to 30 days after completion of treatment of the following selected risks will be collected if available in the medical record. Events will be reported as diagnosed by the investigator:
  - Neurologic adverse events
  - Opportunistic infections
  - **Cytokine release syndrome**
- Time to onset of first specified AEs
- Summary of duration of specified AEs (all events and resolved/recovered events)
- Proportion of Blincyto administrations with medication errors, defined as an unintended failure in the drug treatment process that leads to, or has the potential to lead to, harm to the patient, identified through medical records. Types of medication errors will also be described. Medication errors include:

- incorrect Blincyto dose administered/prepared (eg, drug concentration, device issues, treatment according to SmPC)
- does not include treatment related to dexamethasone

### 9.3.2.2 Secondary Endpoint/Outcomes

#### *Adverse events*

- Incidence of all AEs collected in this study (see Sections 11.2.1 to 11.2.3) (overall, and by severity and seriousness) occurring during blinatumomab treatment and up to 30 days after completion of treatment
- Incidence of specified AEs and all AEs collected in this study (see Sections 11.2.1 to 11.2.3) among patient subgroups defined by demographic and clinical factors (described in Section 9.7.2.3.4)

#### *Efficacy*

- Proportion of patients achieving CR (defined as < 5% bone marrow blasts, platelets > 100,000 cells per  $\mu\text{L}$ , and absolute neutrophil count > 1,000 cells per  $\mu\text{L}$ ) within 2 cycles of Blincyto treatment
- Proportion of patients achieving CR/CRh\*/Cri
- CR defined as < 5% bone marrow blasts, platelets > 100,000 cells per  $\mu\text{L}$ , and absolute neutrophil count > 1,000 cells per  $\mu\text{L}$ , or
  - CRh\* defined as  $\leq$  5% bone marrow blasts, platelets > 50,000 cells per  $\mu\text{L}$ , and absolute neutrophil count > 500 cells per  $\mu\text{L}$ , or
  - CRi defined as  $\leq$  5% bone marrow blasts and incomplete recovery of peripheral blood counts) within 2 cycles Blincyto treatment
- Proportion of patients receiving allogeneic HSCT. Defined for the subset of subjects who achieved CR.
- 1-year and 100-day mortality proportion after allogeneic HSCT. Defined for the subset of subjects who achieved CR.
- Relapse-free survival (RFS) time – defined as time from CR/CRh\*/CRi until relapse (proportion of blasts in bone marrow > 5% or blasts in peripheral blood after documented CR/CRh\*/CRi) or death. Defined for the subset of subjects who achieved CR.
- Disease free survival (DFS): defined as time from initiation of Blincyto (for minimal residual disease-positive [MRD+] patients at Blincyto initiation) until date of relapse or death
- Overall survival (OS) time – defined as time from initiation of Blincyto until death
- Proportion of patients with MRD among those who achieve CR/CRh\*/CRi within two cycles of Blincyto treatment - hematologic MRD detected by polymerase chain reaction (PCR) (or flow cytometry) at a level of  $1 \times 10^{-4}$  or higher.
- Efficacy outcomes (as described above) among patient subgroups defined by demographic and clinical factors (described in Section 9.7.2.3.4)

*Blinicyto utilisation & select health care resource use*

- Blincyto utilisation, for example:
  - Duration of Blincyto use (eg, number of completed cycles, total number of days of Blincyto administration)
  - Dosing pattern (eg, proportion of patients with step-up on day 8, number of cycles initiated, frequency of bag changes)
  - Proportion of patients with treatment changes (eg, interruption, discontinuation, dose reduction) as indicated by the SmPC after AEs (stratified by type of event)
- Select healthcare resource use, for example:
  - Setting of bag changes (eg, in the hospital, in the outpatient clinic, or at home)
  - Total number of days of inpatient Blincyto treatment
  - Proportion of treatment days that were inpatient
  - Incidence of hospitalization not related to infusion during the time of Blincyto treatment and up to 30 days after completion
  - Length of hospital stay not related to infusion during the time of Blincyto treatment and up to 30 days after completion.

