## 2. List of Abbreviations

| Abbreviations | Definition of the Terms  |
|---------------|--|
| AE            | Adverse event  |
| ALL           | Acute lymphoblastic leukaemia  |
| BITE®         | Bispecific T-cell engagers   |
| BSA           | Body surface area  |
| CHMP          | Committee for Medicinal Products for Human Use                             |
| CNS           | Central nervous system   |
| CR            | Complete remission   |
| CRh*          | Complete remission with partial recovery of peripheral blood counts        |
| CRi           | Complete remission with incomplete recovery of peripheral blood counts     |
| CTCAE         | Common Terminology Criteria for Adverse Events                             |
| DFS           | Disease-free survival  |
| EA            | Expanded access  |
| eCRF          | Electronic case report form  |
| EDC           | Electronic data capture system   |
| EMA           | European Medicines Agency  |
| ENCePP        | European Network of Centres for Pharmacoepidemiology and Pharmacovigilance |
| EU            | European Union   |
| GVP           | Good Pharmacovigilance Practices   |
| HIV           | Human immunodeficiency virus   |
| HSCT          | Haematopoietic stem cell transplantation                                   |
| IEC           | Independent ethics committee   |
| IRB           | Institutional review board   |
| KM            | Kaplan-Meier   |
| LFR           | Late first-relapse   |
| MAH           | Marketing Authorisation Holder   |
| MedDRA        | Medical Dictionary for Regulatory Activities                               |
| MRD; MRD+     | Minimal residual disease; minimal residual disease positive                |
| OS            | Overall survival   |
| PASS          | Post-authorisation safety study  |
| PCR           | Polymerase chain reaction  |
| Ph-           | Philadelphia chromosome-negative   |
| PRAC          | Pharmacovigilance Risk Assessment Committee                                |
| PSUR          | Periodic safety update report  |
| RFS           | Relapse-free survival  |
| R/R           | Relapsed or refractory   |
| SAE           | Serious adverse event  |
| SmPC          | Summary of Product Characteristics   |
| TEAE          | Treatment emergent adverse event   |

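### CR is set at < 5% marrow blasts while CRh* and CRi allow ≤ 5% and relapse is > 5%, so a patient at exactly 5% with fully recovered counts can only be CRh* and leaves the CR proportion and the CR-only HSCT denominator

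*Protocol*

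**What the plan says.** The definitions are in the Efficacy part of protocol Section 9.3.2.2.

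- **CR:** "CR (defined as < 5% bone marrow blasts, platelets > 100,000 cells per" µL, with neutrophils above 1,000 per µL. CR is defined twice in the section, with < 5% both times.
- **CRh\*:** the sign changes to ≤, followed by "5% bone marrow blasts, platelets > 50,000 cells per" µL, with neutrophils above 500 per µL. These count limits are lower bounds only. Section 2 expands the term as "Complete remission with partial recovery of peripheral blood counts".
- **CRi:** again ≤, followed by "5% bone marrow blasts and incomplete recovery of peripheral blood counts".
- **Relapse:** "proportion of blasts in bone marrow > 5% or blasts in peripheral blood after documented" CR, CRh* or CRi.

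The section then sets populations. One endpoint reads "Proportion of patients receiving allogeneic HSCT. Defined for the subset of subjects who achieved CR". Mortality after HSCT and RFS carry the same restriction to CR, although RFS time is counted from CR/CRh*/CRi. The MRD proportion uses everyone in CR/CRh*/CRi within two cycles.

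Section 9.7.2.3.2 analyses mortality after HSCT in all patients who undergo an allogeneic HSCT, without requiring CR.

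**The concern.** By their names, the three remission categories differ in how far the blood counts have recovered. As written, CR also differs from the other two in its marrow limit, and only at one value: exactly 5%. There, a patient whose counts clear the CR limits is refused CR on the marrow result and falls into a category named for partial count recovery.

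At stake is the CR proportion, together with any endpoint whose population is CR only. Section 9.9 says that clinical-trial and historical data will give context to the results, so the CR boundary should be coherent. It matters most in the late-first-relapse subgroup, which was included at CHMP's request to inform benefit-risk and is expected to hold only about 42 patients (Section 9.5, Table 1). Because the protocol has already fixed the cut-offs, this is a conflict between stated rules and not detail left for the statistical analysis plan.

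**Working it through.** **The plan's own figure.** Section 9.5 gives 67.6% to 92.4% for an observed CR/CRh* proportion of 80% in 40 patients. The normal-approximation half-width is 1.96 × √(0.80 × 0.20 / 40) = 0.124, giving 67.6% to 92.4%. It reproduces, as do all 24 cells of Table 3. There is no arithmetic error; the issue is in the definitions.

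**Applying the definitions.** Take platelets of 150,000 per µL and neutrophils of 2,000 per µL, both above the CR limits, and vary only the marrow result. CRi is read as requiring counts below the CR limits.

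| Marrow blasts | CR (< 5%) | CRh* (≤ 5%) | CRi (≤ 5%, incomplete counts) | Marrow relapse (> 5%) |
|---|---|---|---|---|
| 4.9% | yes | yes | no | no |
| 5% | no | yes | no | no |
| 5.1% | no | no | no | cut-off crossed |

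At 4.9% the patient meets both CR and CRh*, and the better category is CR. At 5% only CRh* is left, with unchanged counts. With partially recovered counts (75,000 and 800) the result is the same at 4.9% and at 5%, so the anomaly is confined to fully recovered counts.

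**Which endpoints lose the patient at 5%.**

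| Endpoint | Effect |
|---|---|
| CR proportion | no longer counted as a responder |
| HSCT receipt | out of the denominator (CR only) |
| Mortality after HSCT | out under Section 9.3.2.2; kept, if transplanted, under Section 9.7.2.3.2 |
| RFS | out by the CR restriction; in by the start point, which includes CRh* and CRi |
| CR/CRh*/CRi composite, MRD | kept |
| OS, DFS | do not depend on remission category |

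**Size per patient.** One reclassified patient moves the CR proportion by 100/n points:

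- n = 40: 100/40 = 2.5 points
- n = 130: 100/130 = 0.77 points
- n = 200: 100/200 = 0.5 points
- n = 300: 100/300 = 0.33 points

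The first size is the subgroup size used for precision in Section 9.5. The others are the theoretical number of adults with R/R disease, the target in authorised indications, and the overall maximum.

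**Illustrative range.** The protocol does not say how many patients will be recorded at exactly 5% with CR-level counts. If the share were 1% to 5% (assumption), that would be 0.01 × 200 = 2 to 0.05 × 200 = 10 patients of 200, or 0.4 to 2 of 40. The CR proportion would shift by 1 to 5 points. Table 3's half-widths at a proportion of 50% are 6.9 points for n = 200 and 15.5 for n = 40.

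**The case against.** The case for leaving the text alone is that one boundary value of a secondary endpoint is affected, in a descriptive study whose primary endpoints are safety and medication errors. The composite does not change, and no stand-alone CRh* proportion is listed that could be distorted. The protocol nowhere states that the categories must share a marrow limit. The cut-off may also rarely be applied numerically: Appendix B asks for treatment response before and after each cycle where it is recorded in local practice. Section 9.3.3 lists marrow blast percentage only at Blincyto initiation, and no post-cycle marrow percentage is listed as a separate item.

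Most of this stands, and it keeps the priority low. It does not remove the conflict: a category named for partial recovery still takes in a patient with full recovery, and no text says that this is intended.

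Three stronger readings are tempting but not supported:

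- A reader might infer that the relapse rule also includes 5%. It does not. Relapse is > 5% and agrees with the ≤ 5% remission limit.
- A reader might infer that the patient is lost from every CR-based endpoint. Only the CR proportion and HSCT receipt are unambiguous. For mortality after HSCT and RFS the protocol gives two answers.
- A reader might infer that the CR proportion will be materially too low. No share at exactly 5% is given, nor how charts round marrow results. Even the top of the assumed range, 5 points, lies within the 6.9-point half-width at n = 200.

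**Conclusion.** The marrow cut-offs in Section 9.3.2.2 are inconsistent, and CR is the outlier. A patient at exactly 5% blasts with CR-level counts is classed as CRh*, leaves the CR proportion and drops out of the HSCT-receipt denominator. The direction for CR is downward. The direction for HSCT receipt depends on whether the excluded patients were transplanted.

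The effect is 0.5 points of CR per such patient at n = 200 and 2.5 points at n = 40. These figures assume that all n patients are in the CR denominator; 200 spans all authorised indications, including MRD+ disease, so the actual denominator may be smaller and the shift per patient larger. The total effect cannot be sized from the protocol.

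The same section leaves the responder set for RFS and mortality after HSCT unsettled, so the consequence for those two endpoints cannot be stated until that is resolved. Which blast limit is clinically right is not judged here. The point is minor but should be corrected.

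**What to change.** In Section 9.3.2.2, give CR, CRh* and CRi the same marrow limit, make relapse its exact complement, and state that the remission category is then assigned by blood counts, taking the best category met. Either consistent pair resolves the conflict: ≤ 5% with relapse > 5%, or < 5% with relapse ≥ 5%. If the remission limit became < 5% while relapse stayed at > 5%, a patient at exactly 5% would be neither in remission nor relapsed. If the present difference is intended, say so and give the reason.

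In the same edit:

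- State whether RFS covers patients in CR only or in CR/CRh*/CRi.
- Make the population for mortality after HSCT the same in Sections 9.3.2.2 and 9.7.2.3.2.
- State that the harmonised definition applies where response is abstracted as charted.

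The cost is a short change to the definitions. Re-deriving response for patients already abstracted is possible only where a post-cycle marrow blast percentage was recorded; Appendix B does not list that item separately, so the eCRF should be checked first.

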## 6. Milestones

For the timely sharing of the collected data, enrolment updates will be given with each periodic safety update report (PSUR), and analysis of interim data will be performed annually and reported through the respective timetable for the PSURs, defined as per regulatory requirements. Considering the staggered launch of Blincyto and the time taken to recruit sites, it is anticipated that the first interim report will coincide with the subsequent PSUR occurring at least 12 months after start of data collection.

After the last medical record abstraction has been completed, a final data analysis will be performed and a final report summarising the results of the study will be completed and submitted to Regulatory Agencies as appropriate within 12 months after end of data collection.

| Milestone                           | Planned date   |
|-------------------------------------|--|
| Start of data collection            | Q1 2017  |
| End of data collection              | Approximately 7 years after start  |
| Enrolment updates                   | With each PSUR   |
| Interim reports                     | Annually starting from the subsequent PSUR occurring at least 12 months after start of data collection |
| Registration in the EU PAS register | Before start of data collection  |
| Final report of study results       | Within 12 months after end of data collection  |

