## 7. Rationale and Background

### 7.1 Diseases and Therapeutic Area

Acute lymphoblastic leukaemia (ALL) is a rare malignant disease with an overall incidence of 1.1/100,000 per year. ALL has a bimodal distribution with an early peak at 4 to 5 years of age (incidence of 4.5/100,000 per year) followed by a second gradual increase starting at 50 years and increasing in the 80s (incidence of 2/100,000 per year). It represents 80% of acute childhood leukaemia and 20% of acute leukaemia cases in adults (Pui and Evans 2006; Jabbour et al, 2005; Larson, 2005; SEER, 1975-2009 (Accessed July 2012)). In adults with relapsed or refractory (R/R) B-precursor ALL, treatment options are limited and the prognosis unfavourable. Primary refractory ALL is defined by absence of complete remission (CR) after standard induction therapy. A patient has relapsed ALL if they achieved a CR during upfront therapy and has then relapsed during or after completion of therapy. A similar classification is possible for salvage therapy. Refractory relapse is defined by lack of CR after first salvage therapy. Second relapse or later relapses are defined as relapse after achieving a second CR in

first salvage or later salvage therapies. Currently the only curative option for patients with ALL is allogeneic haematopoietic stem cell transplant (HSCT), which is performed once CR is achieved. Therefore, new therapies that can improve the likelihood of CR are important.

Blinicyto belongs to a new class of bispecific antibody constructs called bispecific T-cell engagers (BiTE®). BiTEs® have been designed to direct T-effector memory cells towards target cells. The proximity induced by the BiTE® triggers target cell-specific cytotoxicity, which closely resembles standard cytotoxic T lymphocyte activation. Blincyto is administered as an intravenous infusion with a single cycle of treatment consisting of 4 weeks of continuous infusion followed by 2 weeks without Blincyto treatment. Blincyto is administered at one of two different dosages (depending on the point in time of the patient's treatment). During Cycle 1, Blincyto is administered at a dose of 9 µg/day on Days 1-7 and 28 µg/day on Days 8-28. A treatment course consists of 2 cycles of Blincyto for induction. Patients who have achieved CR/CRh\* after 2 treatment cycles may receive 3 additional cycles for consolidation treatment.

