#### **9.4 Data Sources**

All data for this study will be abstracted from patient medical records by site staff using chart reviews at the treatment centre where Blincyto was initiated. The data from these chart reviews will be merged to form a longitudinal cohort for analysis. Since these are data that are collected for patient care, information on Blincyto administration and AEs (eg, type of event, dates of onset, and resolution and severity) are expected to be reasonably complete, although some missing data can be expected. Evaluations of efficacy of treatment, concomitant medications, patient history (including comorbid conditions), and other patient information are also important for patient care and are expected to be available in the medical record.

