### **9.7.2 Planned Method of Analysis**

All analyses will be descriptive. Continuous variables will be summarised by mean, median, standard deviation, 25th percentile, 75th percentile, minimum and maximum. Categorical variables will be summarised by number and percentage. For categorical outcomes, 95% confidence intervals will also be presented where appropriate. For time-to-event endpoints, Kaplan-Meier (KM) curves and estimates (median, 1st and 3rd quartile) of the time-to-event endpoint with 95% confidence intervals will be calculated, if estimable. Six, 12- and 24-month survival proportions and 95% confidence intervals will also be estimated. Tables will be presented for the total patient population (ie, those who meet the eligibility criteria and have at least one dose of Blincyto) split by adult and paediatric patients and for disease subgroups with 15 or more patients, as well as for the subset of patients with LFR. Safety and efficacy data will also be tabulated by the patient subgroups described in Section [9.7.2.3.4](#).

The Medical Dictionary for Regulatory Activities (MedDRA) version 24.1 or later will be used to code all adverse events.

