### 13. Plans for Disseminating and Communicating Study Results

Common study protocol, study status, and report(s) will be included in regulatory communications in line with the risk management plan, PSURs, and other regulatory milestones and requirements. Interim reports will be provided as part of PSUR procedures, and will include descriptive analyses and results for the primary and secondary objectives. Any safety concerns that may be identified during interim analyses will be immediately communicated to regulatory authorities in accordance with GVP. Any new information that may affect the risk-benefit balance of the medicinal product would be communicated immediately in writing as an Emerging Safety Issue to competent authorities of the Member States in which the product is authorised and to the Agency via email. The final study report will be completed within one year after the end of data collection, and will be prepared regardless of whether the study is completed or prematurely terminated. The final study report will be submitted to the EMA and to the respective Competent Authorities as applicable. The summary of the final results will be provided to all participating HCPs. Any manuscript and/or abstract for scientific presentation(s) will be developed and submitted in accordance in with the *2012 Guideline on Good Pharmacovigilance Practice (GVP): Module VIII – Post-Authorisation Safety Studies* (EMA, 2017 module VIII).

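### Transplant receipt among CR patients is an open-ended crude percentage, so interim and country figures tend to be too low where follow-up is short

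*Protocol*

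**What the plan says.** Section 9.3.2.2 (Efficacy) lists "Proportion of patients receiving allogeneic HSCT. Defined for the subset of subjects who achieved CR". The endpoints around it carry a window: CR is assessed "within 2 cycles of Blincyto treatment", and mortality after HSCT is taken at 100 days and 1 year. HSCT receipt has none.

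Section 9.7.2 summarises categorical variables by number and percentage and keeps Kaplan-Meier for time-to-event endpoints. On the reporting population it says "Tables will be presented for the total patient population (ie, those who meet the eligibility criteria and have at least one dose of Blincyto"; no minimum observation is attached. Section 9.7.2.3.2 applies Kaplan-Meier rates to mortality after HSCT, but names no method for reaching HSCT that allows for incomplete follow-up.

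On timing:
- Section 9.2.1 includes new patients for 5 years and plans at least 2 years of follow-up each.
- Section 6 states that "analysis of interim data will be performed annually".
- Section 13 adds: "Interim reports will be provided as part of PSUR procedures, and will include descriptive analyses and results for the primary and secondary objectives".
- Section 9.2.4 lists, among the events that close a patient's record, "end of available data in the chart, or end of study".
- Section 9.4 limits the source to abstraction "using chart reviews at the treatment centre where Blincyto was initiated".
- Section 9.7.2.3.4 tabulates efficacy by country, and Section 9.2.2 expects a staggered launch.

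**The concern.** The denominator is every patient in CR and the numerator is every transplant recorded so far. A patient who reached CR a month before the data cut, or whose chart stops soon after CR, enters as not transplanted, exactly like a patient followed for years without one. The percentage therefore mixes how often patients reach transplant with how long they have been watched.

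Two uses are exposed. Interim figures taken while inclusion is open are weighted towards recently treated patients. Country rows in one table can differ only because one country opened later. Section 7.1 describes allogeneic HSCT as the only curative option, so readers will look at this endpoint. The protocol already allows for incomplete follow-up after transplant but not on the way to it.

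**Working it through.** **Inputs from the protocol.** Inclusion lasts 5 years and follow-up is at least 2 years (Section 9.2.1). Reports are annual (Section 6). A cycle is 6 weeks: "a single cycle of treatment consisting of 4 weeks of continuous infusion followed by 2 weeks without Blincyto treatment" (Section 7.1). The protocol states no expected HSCT proportion, so there is no figure of its own to reproduce here.

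**Assumptions, none from the protocol.** The eventual HSCT proportion among CR patients is π = 50%, with 30% as an alternative. Time from CR to HSCT follows a gamma distribution with shape 2 and median m = 2, 4 or 6 months, so its scale is θ = (m/12)/1.678 years. Of responses, 75% are recorded at 6 weeks and 25% at 12 weeks. Entry is uniform from study start, nobody enters with mature data, and no chart ends early. The CR rate cancels, because the denominator holds only patients already in CR.

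**Formula.** For a cut at T ≤ 5 years and a response at time t after initiation, time from CR to the cut is uniform on 0 to L = T − t. The expected share of eventual transplants already recorded is

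R(L) = 1 − 2θ/L + (1 + 2θ/L)·exp(−L/θ).

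The crude figure is π times the average of R, weighted by (share of responses) × L.

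**Worked case, m = 4 months, θ = 0.1986.**
- Year 1: responses at 6 weeks have L = 0.885 and R = 0.568; at 12 weeks L = 0.770 and R = 0.515. The weights are 0.75 × 0.885 = 0.664 and 0.25 × 0.770 = 0.193. The average is (0.664 × 0.568 + 0.193 × 0.515)/0.857 = 0.556, and 50% × 0.556 = 27.8%.
- Year 5: R = 0.919 (L = 4.885) and 0.917 (L = 4.770), which gives 45.9%.

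A simulation on the same assumptions agrees (28.0% and 46.1%). Its full results for π = 50% are:

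| Median CR to HSCT | Yr 1 | Yr 2 | Yr 3 | Yr 4 | Yr 5 | Yr 6 | Yr 7 |
|---|---|---|---|---|---|---|---|
| 2 months | 38.1 | 44.3 | 46.1 | 47.2 | 47.7 | 49.7 | 49.7 |
| 4 months | 28.0 | 39.6 | 43.3 | 45.0 | 46.1 | 50.0 | 50.2 |
| 6 months | 20.0 | 33.9 | 39.6 | 42.3 | 43.9 | 49.1 | 49.9 |

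The shortfall is about 12 to 30 points at year 1 and 2 to 6 points at year 5. With π = 30%, the crude figure is 12.0-23.0% at year 1 and 26.3-28.8% at year 5.

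**Accrual shape.** If accrual doubles yearly (π = 50%, 4 months), years 1 to 5 read 25.2, 34.5, 37.0, 37.8 and 38.0%. The trend flattens, but the year-5 shortfall grows to 12 points.

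**Country rows.** At a year-5 cut with a 4-month median, a country open for all 5 years would read about 46.1% and one open for the last year about 28.0%. That is 18.1 points apart with the same true 50%.

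**Early chart end.** If a share c of CR patients have charts that end before a transplant could be recorded, and they would otherwise have reached the same 50%, the final crude figure is 50% × (1 − c). That is 47.5% for c = 5% and 40% for c = 20%. These values of c are illustrations.

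**The case against.** **The final result.** A reader might infer that the endpoint is understated outright. With complete charts it is not: the modelled figure at year 7 is 49.7-50.2% of a true 50%, because 2 years of follow-up is long against medians of 2 to 6 months. This stands. Only early chart end leaves a shortfall in the final report, and its extent is unknown.

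**The trend.** A reader might also infer that the figures must rise from report to report. They need not. With 300 patients, 40% in CR and uniform accrual, the chance of an observed rise at every report in years 1 to 5 is only about 14-34%, and accelerating accrual flattens the trend. The downward bias is in expectation. Sampling error is large beside it: with π = 50% the standard error is about 10.2 points at 60 patients treated and 4.6 at 300.

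**CR within 2 cycles.** It is tempting to extend the point to this endpoint. The documents do not support that. CR has a fixed window of about 12 weeks, and nothing says that a patient still in cycle 1 or 2 at a cut counts as a non-responder. Interim evaluability rules may also sit in the SAP, which is not at hand.

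**Mature entrants.** The study is a retrospective record review (Section 9.1), and patients may already have been treated before entry (Section 9.3.1). Some enter with long histories, so the year-1 figures are an upper-end illustration.

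**Timing.** Collection began in Q1 2017, so 5 years of inclusion nominally ended in Q1 2022, before this version of 9 September 2022. The years of largest modelled bias have passed, unless the inclusion period is extended as Section 9.5 permits. This limits the practical gain.

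**Descriptive only.** No comparative analysis is planned. That removes formal tests but does not stop a reader comparing country rows printed together.

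**Conclusion.** The point holds for HSCT receipt. As the protocol fixes it, the endpoint has no horizon and no allowance for unequal follow-up, so interim and country-level proportions tend to be too low where follow-up is short. Under the stated assumptions the crude value for a true 50% is about 20-38% at year 1 and 44-48% at year 5. Once inclusion has closed and follow-up is complete, the bias is negligible unless charts end early.

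The sizes rest wholly on assumed transplant rates and timing; the direction does not. The choice lies in the protocol's own endpoint definition and summary rule, and an SAP that followed them would produce the crude figure. This is a modest but worthwhile correction to one descriptive secondary endpoint. It matters most for any interim or country table made while inclusion is open or extended, and for charts that stop early.

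**What to change.** In Sections 9.3.2.2 and 9.7.2.3.2, report the cumulative incidence of allogeneic HSCT at fixed times from response, for example 6 and 12 months, with 95% confidence intervals. Treat death without HSCT as a competing event and censor at end of chart data or data cut. This matches in spirit the Kaplan-Meier approach already used after HSCT. Keep the crude count and percentage alongside, and use the same estimator in the country table.

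The cost is some extra programming; response, HSCT and death are already collected. One limit remains: if a patient leaves the initiating centre to be transplanted elsewhere, censoring at chart end is informative and the estimate is not fully repaired. Each table should therefore also show how many CR patients have charts that end before the horizon.
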